### **8.8.1 Samples for Research Biosample Repository**

#### **8.8.1.1 Overview of the Research Biosample Repository**

The RBR is a centrally administered group of facilities for the long-term storage of human biologic specimens, including body fluids, solid tissues, and derivatives thereof (e.g., DNA, RNA, proteins, peptides). The collection, storage, and analysis of these specimens will facilitate the rational design of new pharmaceutical agents and the development of diagnostic tests, which may allow for individualized drug therapy for patients in the future.

Specimens will be collected from participants who give specific consent to participate in this optional RBR. Collected specimens will be used to achieve the following objectives:

- To study the association of biomarkers with efficacy, AEs, or progressive disease
- To increase knowledge and understanding of disease biology
- To study treatment response, including drug effects and the processes of drug absorption and disposition
- To develop biomarker or diagnostic assays and establish the performance characteristics of these assays.

#### **8.8.1.2 Sample Collection**

RBR samples will be collected at the time-point indicated in the SoA (Section 1.3). The following samples will be stored in the RBR and used for research purposes, including, but not limited to, research on biomarkers related to RO7049389 or diseases:

- RBR blood sample

For all samples, dates of consent and specimen collection should be recorded on the associated Research Biosample Repository page of the eCRF. For sampling procedures, storage conditions, and shipment instructions, see the separate Laboratory Manual.

RBR specimens will be stored and used until no longer needed or until they are exhausted. The Research Biosample Repository storage period will be in accordance with the IRB/EC-approved Informed Consent Form and applicable laws (e.g., Health Authority requirements).

The repository specimens will be subject to the confidentiality standards (as described under Confidentiality and in [Appendix 1](#)).

### **8.9 HEALTH ECONOMICS**

Health Economics/Medical Resource Utilization and Health Economics parameters are not evaluated in this study.

### **8.10 TIMING OF STUDY ASSESSMENTS**

#### **8.10.1 Screening and Pre-treatment Assessments**

Written informed consent for participation in the study must be obtained before performing any study-specific screening tests or evaluations. Informed Consent Forms (ICFs) for enrolled participant and for participants who are not subsequently enrolled will be maintained at the study site.

All screening and pre-treatment assessments must be completed and reviewed to confirm that participants meet all eligibility criteria. The Investigator will maintain a screening log to record details of all participants screened and to confirm eligibility or record reasons for screening failure.

An Eligibility Screening Form (ESF) documenting the Investigator's assessment of each screened participant with regard to the protocol's inclusion and exclusion criteria is to be completed by the Investigator and kept at the investigational site.

#### **8.10.2 Assessments during Treatment**

Under no circumstances will participants who enroll in this study and have completed treatment as specified, be permitted to re-enroll in the study.

All assessments must be performed as per SoA (see Section 1.3). Assessments scheduled on the day of study treatment administration should be performed prior to administration of study treatment, unless otherwise noted in the schedule of assessments.

#### **8.10.3 Assessments at Study Completion/Early Termination Visit**

Participants who complete the last dose administration or discontinue from the study early will be asked to return to the clinic 7 days after the last dose of study treatment for a follow-up visit and 28 days after the last dose of study treatment for a follow-up call. The follow-up visit and follow-up call will be reported as the study completion visit in eCRF

In case of early termination of a participant, a blood sample for PK assessment of RO7049389 and pitavastatin should be collected at the time of discontinuation. Please also see Section 1.3 for activities that are required to be performed in case of an early termination.

#### **8.10.4 Follow-Up Assessments**

After the study completion/early termination visit, adverse events should be followed as outlined in Sections 8.3.1 and 8.3.3.

#### **8.10.5 Assessments at Unscheduled Visits**

Please see Section 1.3 for activities that are required to be performed in case of an unscheduled visit.

If an unscheduled visit is required to ensure safety of study participants, necessary assessments will be undertaken at the discretion of the Investigator. All unscheduled assessments should be reported in eCRF.

Unscheduled local laboratory tests may be ordered per Investigator's discretion and may be used for the individual management of study participants.

### **9. STATISTICAL CONSIDERATIONS**

The primary objective of this study is to characterize the pharmacokinetics profile of pitavastatin in healthy participants following multiple dose of RO7049389 on the single-

dose of pitavastatin. Statistical summaries will be descriptive in nature. All participants who receive any amount of study medication will be included in the safety analysis.

## **9.1 STATISTICAL HYPOTHESES**

Not Applicable

## **9.2 SAMPLE SIZE DETERMINATION**

A sample size of 18 participants to target 16 evaluable healthy participants has been chosen. Evaluable participants who withdraw for non-safety reasons from the study will be replaced to meet the enrollment goal.

Assuming a coefficient of within participant variation of 30% for  $C_{max}$  and AUC, with a sample size of 16 evaluable participants per period, the entire 90% confidence interval for a geometric mean ratio (using pitavastatin alone as the reference) in the  $C_{max}$  and AUC will be entirely within a range from 80% to 125% of the true (but unknown) geometric mean ratio with a probability of at least 80% (i.e., estimation power).

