### **4.2 SCIENTIFIC RATIONALE FOR STUDY DESIGN**

The study rationale is provided in Section [2.1](#).

This is an open-label, fixed sequence, two-period study.

The primary objective of this study is to determine the effect of multiple-doses of RO7049389 on the single-dose PK of pitavastatin in healthy participants. As PK measurements are objectively analysed an open-label study design has been chosen. To minimize the number of participants needed and reduce inter-subject variability, this study will follow a two-period instead of parallel design. The duration of both washout and drug administration periods was established on the basis of the known

pharmacokinetic profiles of both RO7049389 and pitavastatin. The half-life [REDACTED] of RO7049389 was used to calculate the likely time needed for steady state and that of pitavastatin was used to calculate the duration needed to capture its entire elimination phase. To ensure the full potential for an interaction is realized (maximal inhibition of OATP), pitavastatin will be co-administered with RO7049389 while the latter is in steady state. Administration of RO7049389 will be continued throughout the whole elimination phase of pitavastatin. Accordingly, a fixed sequence design has been chosen for logistical reasons.

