**9.4.3 Pharmacokinetic Analyses**

Analyses will be carried out on the PK analysis population.

Individual and mean plasma concentrations at each sampling time-point for RO7049389 and its metabolites (RO7121986, RO7255420 and RO7255422), pitavastatin and pitavastatin lactone as appropriate will be presented by listings and descriptive summary statistics, including means, geometric means, ranges, standard deviations and coefficients of variation. Individual and mean concentration versus time will be plotted on semi-logarithmic scales.

Non-compartmental analysis will be employed for estimation of PK parameters. All PK parameters will be presented by individual listings and summary statistics for each period including means, geometric means, medians, ranges, standard deviations and coefficients of variation.

To assess the effect of RO7049389 on the PK of pitavastatin, the logarithmically transformed variables  $C_{max}$  and  $AUC_{0-inf}$  of pitavastatin and its metabolite pitavastatin lactone will be subjected to an ANOVA (with factors RO7049389 and participant) for which measurements are available for healthy participants in both with/without

RO7049389. 90% confidence intervals for the ratio of geometric means will be calculated using the pitavastatin alone as the reference.

The same analysis of variance will be applied to the secondary parameters  $AUC_{0-12hr}$  and  $C_{max}$  of RO7049389 and its metabolites (RO7121986, RO7255420 and RO7255422) to assess the effect of pitavastatin on the PK of RO7049389.

In case  $AUC_{0-inf}$  cannot be determined reliably, an appropriately truncated AUC will be used.

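### Section 9.2 claims at least 80% probability that the 90% CI lies within 80–125% of the true ratio; its own inputs give about 33%

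*Combined protocol and SAP*

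**What the plan says.** Section 9.2 gives every input. The size is set as "A sample size of 18 participants to target 16 evaluable healthy participants has been chosen", and the precision statement is made "with a sample size of 16 evaluable participants per period". The variability assumption is "Assuming a coefficient of within participant variation of 30% for" Cmax and AUC. The quantity of interest is "the entire 90% confidence interval for a geometric mean ratio (using pitavastatin alone as the reference"), and the claim is that this interval will be "entirely within a range from 80% to 125% of the true (but unknown) geometric mean ratio with a probability of at least 80" per cent. The section calls this estimation power.

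The design and analysis are fixed elsewhere. Section 4.2 says "This is an open-label, fixed sequence, two-period study", so each participant supplies both measurements. Section 9.4.3 says the log-transformed parameters "will be subjected to an ANOVA (with factors RO7049389 and participant"), with a 90% interval for the ratio against pitavastatin alone. The documents give no formula, no software and no source for the 30%.

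**The concern.** The claim concerns the entire interval and is centred on the true ratio. For it to hold, the half-width plus the error of the point estimate must stay below ln 1.25. With 16 pairs and a CV of 30%, the expected half-width alone uses about four-fifths of that allowance (0.182 / 0.223 = 0.82), so a probability of 80% or more is not plausible.

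Section 9.1 sets no hypothesis and Section 9 describes the summaries as descriptive, so this sentence is the only quantitative basis for the sample size. Section 2.3 says the results are to guide statin dosing with RO7049389. A reader of Section 9.2 would expect the whole 90% interval to stay within 80–125% of the truth in at least four of five such studies.

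**Working it through.** **Inputs, all from the protocol.** n = 16 participants measured in both periods; within-participant CV 30%; two-sided 90% interval; limits 80% and 125% of the true ratio (Section 9.2). Log scale, ANOVA with treatment and participant (Section 9.4.3), hence 15 residual degrees of freedom.

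**Components.**
- Within-participant log SD: σ = √ln(1 + 0.30²) = √ln 1.09 = 0.2936.
- Standard error of the log ratio: σ√(2/n) = 0.2936 × √(2/16) = 0.1038. The 2 is there because the ratio compares two measurements per participant.
- t(0.95, 15) = 1.753.
- Expected half-width: 1.753 × 0.1038 = 0.182, so the expected interval is about 0.83 to 1.20 times the estimate.
- Limit: ln 1.25 = 0.2231.
- Room left for error in the estimate: 0.2231 − 0.1819 = 0.041, or 0.4 standard errors.

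**Rough check.** With the half-width held at 0.182, the probability is 2Φ(0.397) − 1 = 0.309.

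**Exact value.** Let d be the error of the estimated log ratio, and let the estimated standard error be 0.1038 × √(χ²₁₅/15). The required probability is P(|d| + 1.753 × estimated SE < ln 1.25). Integrating over the χ² distribution gives **0.328**; a simulation of 2,000,000 draws also gives 0.328.

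**Attempts to reproduce the stated 80%.** All use n = 16.

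| Variant | Probability |
|---|---|
| Exact, as above | 0.328 |
| z quantile, estimated variance | 0.395 |
| z quantile, known variance | 0.387 |
| Noncentral t approximation | 0.316 |
| 14 degrees of freedom | 0.325 |
| Unpaired, 30 degrees of freedom | 0.353 |
| 0.30 used directly as the log SD | 0.299 |
| Only one limit required | 0.658 |
| √2 omitted, exact | 0.790 |
| √2 omitted, known variance, t quantile | 0.802 |
| Half-width below ln 1.25 around the estimate | 0.906 |

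Only the last three come close to 80% or exceed it. Leaving out √2 (standard error 0.2936/4 = 0.0734, half-width 0.129) lands almost on the stated figure. That suggests where it came from but does not prove it.

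**What 80% would take, with the limits at 80–125%.**

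| n (CV 30%) | Probability | | CV (n = 16) | Probability |
|---|---|---|---|---|
| 16 | 0.328 | | 20% | 0.837 |
| 18 | 0.416 | | 20.8% | 0.799 |
| 24 | 0.637 | | 25% | 0.577 |
| 31 | 0.799 | | 30% | 0.328 |
| 32 | 0.816 | | | |

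At n = 16 and CV 30%, the limits met with 80% probability are 72.7% and 137.5%.

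**Both parameters.** The figures above are for one parameter. If the statement is meant to hold for Cmax and AUC together, the probability cannot exceed 0.328 and would be 0.328² = 0.11 if the two were independent. The documents give no correlation.

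**The case against.** The strongest defence is that the sponsor meant something other than what is written. There are two candidates.

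- **Width around the estimate.** If the interval was to lie within 80–125% of the observed ratio, the probability is 0.906 and a claim of at least 80% is true, even conservative. The number would then stand and only the reference to the true ratio would be wrong. But the text names the true, unknown ratio explicitly, so the sentence still needs changing.
- **30% as the CV of the within-participant ratio.** This removes √2 and gives 0.790 at n = 16, and 0.852 if all 18 are evaluable. The text attaches the 30% to Cmax and AUC, not to their ratio, and the exact value at 16 is still just short of 80%.

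It can also be said that little depends on the error. The study is descriptive, there is no pass/fail boundary, and the reported interval will show the precision achieved. The point estimate alone falls within 80–125% of the true ratio with probability 0.968. All of this is correct. It limits the consequence to the planning statement: no estimate is biased and no analysis is affected. It does not make the statement true.

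**Conclusion.** The claim fails on its own inputs. The probability that the whole 90% interval lies within 80–125% of the true ratio is 0.328 with 16 evaluable participants, against a stated 0.80 or more: an overstatement of about 2.4-fold (0.80 / 0.328). With all 18 evaluable it is 0.416. This rests on log-normal data, on the 30% being the within-participant CV of each parameter, and on the paired ANOVA of Section 9.4.3. None of the technical choices tried, short of dropping √2 or changing the criterion, brings it to 80%. Nothing elsewhere in the protocol corrects the figure. Because it is the sole numerical justification for the sample size, it should be corrected, although 16 participants may well give adequate precision for a descriptive interaction study.

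**What to change.** Keep 18 enrolled for 16 evaluable and rewrite the sentence in Section 9.2 in one of two ways.

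1. **Containment around the true ratio:** with 16 evaluable participants and a within-participant CV of 30%, the 90% interval will lie entirely within about 72.7% to 137.5% of the true geometric mean ratio with 80% probability, and within 80–125% of it with probability about 33%.
2. **Width around the observed ratio:** the 90% interval will lie within 80–125% of the observed geometric mean ratio with probability about 0.91 (expected interval about 83% to 120% of the observed ratio). The reference to the true ratio must then be removed.

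If the 30% was meant as the CV of the within-participant ratio, say so and give its source; the exact figure at 16 participants is then 79%. In every case, state the formula or software used and whether the probability applies to each parameter separately.

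The cost is one sentence. No participants, visits or analyses are added. Under option 1 the stated precision becomes less favourable.

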## **9.3 POPULATIONS FOR ANALYSES**

### **9.3.1 Pharmacokinetic Analysis Population**

All participants who have received at least one dose of study treatment (RO7049389 or pitavastatin) and who have data from at least one post-dose sample will be included in the PK analysis population. Participants will be excluded from the PK analysis population if they significantly violate the inclusion or exclusion criteria, deviate significantly from the protocol, or if data are unavailable or incomplete which may influence the PK analysis. Excluded cases will be documented together with the reason for exclusion. All decisions on exclusions from the analysis will be made prior to database closure.

### **9.3.2 Safety Analysis Population**

All participants, who received at least one dose of the study treatment (RO7049389 or pitavastatin), whether prematurely withdrawn from the study or not, will be included in the safety analysis.

For purposes of analysis, the following populations are defined in [Table 5](#).

**Table 5 Analysis Populations**

Population	Description
Safety	All participants, who received at least one dose of the study treatment, whether prematurely withdrawn from the study or not, will be included in the safety analysis.
Pharmacokinetic	All participants who have received at least one dose of study treatment (RO7049389 or pitavastatin) and who have data from at least one post-dose sample will be included in the PK analysis population. Participants will be excluded from the PK analysis population if they significantly violate the inclusion or exclusion criteria, deviate significantly from the protocol, or if data are unavailable or incomplete which may influence the PK analysis. Excluded cases will be documented together with the reason for exclusion. All decisions on exclusions from the analysis will be made prior to database closure.

## **9.4 STATISTICAL ANALYSES**

### **9.4.1 Demographics and Baseline Characteristics**

Descriptive statistics will be used for demographic and baseline characteristics as applicable and will include sex, race (Asian and non-Asian, Chinese among Asian), ethnicity, age, weight, height and body mass index. For continuous variables, mean, standard deviation, median, and minimum and maximum values will be presented. For categorical data, the proportion of participants in each category will be summarized.

### **9.4.2 Safety Analyses**

All safety analyses will be based on the safety analysis population.

**Table 6 Safety Statistical Analysis Methods**

Endpoint	Statistical Analysis Methods
Adverse events	The original terms recorded on the eCRF by the Investigator for adverse events will be coded by the Sponsor. Adverse events will be summarized by appropriate thesaurus level and grouped according to treatment period.
Clinical laboratory tests	All clinical laboratory data will be stored on the database in the units in which they were reported. Participant listings and summary statistics at each assessment time will be presented using the International System of Units (SI units; Système International d'Unités ). Laboratory data not reported in SI units will be converted to SI units before processing.  Laboratory test values will be presented by individual listings with flagging of values outside the reference ranges. See Appendix 4 for details on standard reference ranges and data transformation and the definition of laboratory abnormalities.
Vital signs	Vital signs data will be presented by individual listings with flagging of values outside the normal ranges and flagging of abnormalities. In addition, tabular summaries will be used, as appropriate.
ECG data analysis	ECG data will be presented by individual listings with flagging of values outside the normal ranges and flagging of marked abnormalities. Summary descriptive statistics for the actual values and changes from baseline will be tabulated by nominal time for HR, QRS duration, PR and QTcF.
Concomitant medications	The original terms recorded on the participants' eCRF by the Investigator for concomitant medications will be standardized by the Sponsor by assigning preferred terms.  Concomitant medications will be presented in summary tables and listings.

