## OVERALL STUDY DESIGN

This is an open-label, fixed sequence, two-period (Periods 1 and 2) study designed to evaluate the drug-drug interaction between RO7049389 and pitavastatin and the safety and tolerability of single-dose pitavastatin alone and in combination with multiple-doses of RO7049389 in healthy participants.

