**Table 3 Objectives and Endpoints**

Objectives	Endpoints
Primary	

 
To determine the effect of multiple-doses of RO7049389 on the single-dose pharmacokinetics (PK) of pitavastatin in healthy participants.
 
	
 
Primary PK parameters of pitavastatin: <math>C_{max}</math>, and <math>AUC_{0-inf}</math>
 
Secondary PK parameters of pitavastatin: <math>t_{max}</math>, CL/F, V/F and <math>t_{1/2}</math>.
 
Other parameters may be calculated if considered appropriate.
 

Secondary	

 
To evaluate the safety and tolerability of the single-dose pitavastatin alone and in combination with multiple-doses of RO7049389 in healthy participants.
 
To explore the effect of the single-dose of pitavastatin on steady-state PK of RO7049389 in healthy participants.
 
To determine the effect of multiple-doses of RO7049389 on the single-dose PK of pitavastatin lactone in healthy participants (if applicable).
 
	
 
Incidence and severity of adverse events.
 
Incidence of laboratory abnormalities based on hematology, clinical chemistry, coagulation, lipids, and urinalysis test results.
 
ECGs.
 
Vital signs including blood pressure (BP), pulse rate and body temperature.
 
Primary PK parameters of RO7049389 and its metabolites (RO7121986, RO7255420 and RO7255422): <math>C_{max}</math>, and <math>AUC_{tau}</math>.
 
PK parameters of pitavastatin lactone: <math>C_{max}</math>, and <math>AUC_{0-inf}</math>.
 
The AUC ratio of pitavastatin lactone/pitavastatin.
 

Exploratory	

 
To evaluate the effect of multiple-doses of RO7049389 on OATP activity as assessed by plasma and urine coproporphyrins (CP-I and CP-III).
 
	
 
Coproporphyrins (CP-I and CP-III) AUC in plasma and amount excreted in urine.
 

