#### **4.1.1 Length of the Study**

The total duration of the study for each participant will be about 12 weeks divided as follows:

- Screening: Up to 28 days.
- Period 1:
  - In clinic period: Days -1 to 4.
  - Treatment period: Day 1
- Wash-out Period: Defined as from Period 1 Day 1 to Period 2 Day 1 and lasts at least 7 days but not more than 21 days
- Period 2:
  - In clinic period: Days -1 to 7
  - Treatment period: Days 1 to 6
- Safety follow-up:
  - Period 2 Day 13
  - Period 2 Day 34 (Telephone call)

The participant has the option to stay in clinic during the whole Period 1 and wash-out period if agreed by Sponsor and the Investigator.

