**Table 4 Summary of Treatments Administered**

Study Treatment Name:	RO7049389	Pitavastatin
Dosage Formulation:	Tablet	Tablet
Unit Dose Strength(s):	200 mg	2 mg
Dose:	800 mg BID	2 mg
Route of Administration:	Oral	Oral
Dosing Instructions:	4 tablets to be taken, with food	1 tablet to be taken, with food
Packaging and Labeling:	Study treatment will be provided in labeled bottles.	
Manufacturer	F. Hoffmann-La Roche Ltd	Kowa

Study treatments will be administered orally to the participants by investigational staff for all dosing with still water at room temperature.

Pitavastatin will be administered orally to participants by investigational staff in the morning on Day 1 of Period 1 and Day 4 of Period 2. Thirty minutes before the administration, a standard meal will be served to participants, which should be consumed within thirty minutes. RO7049389 will be administered orally to participants by investigational staff from Day 1 to Day 6 of Period 2 twice daily. The first daily dosing will be administered in the morning and the second daily dose will be in the evening, with approximately 12 hours interval. In the morning of Day 4 of Period 2, pitavastatin will be administered together with RO7049389.

For RO7049389, please see the [RO7049389 Investigator's Brochure](#) for more details.

For pitavastatin, see the local prescribing information for more details.

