### **9.5                SUMMARIES OF CONDUCT OF STUDY**

The number of participants who enroll, discontinue, or complete the study will be summarized. Reasons for premature study withdrawal will be listed and summarized by treatment period. Protocol deviations will be listed and evaluated for their potential impact on interpretation of study results. Study drug administration will be summarized by treatment period. Descriptive statistics will be used in evaluating the conduct of the study.

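### Grouping adverse events by treatment period pools RO7049389 alone with the combination in Period 2, so events that start after pitavastatin is added get no figure of their own

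*Combined protocol and SAP*

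**What the plan says.** The study is an "open-label, fixed sequence, two-period (Periods 1 and 2) study". The first secondary objective in Table 3 is "To evaluate the safety and tolerability of the single-dose pitavastatin alone and in combination with multiple-doses of RO7049389 in healthy participants", and incidence and severity of AEs is one of its endpoints.

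On dosing in Period 2, Section 6.1 states: "RO7049389 will be administered orally to participants by investigational staff from Day 1 to Day 6 of Period 2 twice daily". It adds: "In the morning of Day 4 of Period 2, pitavastatin will be administered together with RO7049389". Section 4.2 explains the overlap: "Administration of RO7049389 will be continued throughout the whole elimination phase of pitavastatin".

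On analysis, the AE row of Table 6 (Section 9.4.2) reads: "Adverse events will be summarized by appropriate thesaurus level and grouped according to treatment period". Section 9.4.2 does not define treatment period. Section 4.1.1 gives Period 2 a single one, "Treatment period: Days 1 to 6". Section 9.5 uses the same term without sub-phases: "Study drug administration will be summarized by treatment period". AEs are collected until 28 days after the last dose (Section 8.3.1), which is Period 2 Day 34.

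**The concern.** The objective sets pitavastatin alone against pitavastatin with RO7049389. A reader of the planned table would naturally take the Period 1 column as the first and the Period 2 column as the second. Yet an AE that starts on Period 2 Day 2 began before pitavastatin was given in that period. In the table it cannot be told apart from one that starts on Day 5.

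The other safety rows of Table 6 do not share the problem in the same way. Laboratory values are summarised at each assessment time and ECGs by nominal time, so those results can be separated by day. The AE row has no planned separation in time within Period 2. At stake is how well the AE table describes tolerability after the two drugs are combined.

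**Working it through.** The plan states no figure on this point to reproduce. The check sets the grouping against the dosing schedule and then asks how far the pooled figure can depart from the one of interest.

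**1. Does the Period 2 group really mix two exposures?** Two readings of treatment period fit the text:
- *Dosing days only (Section 4.1.1).* Period 2 is Days 1 to 6. AEs on Period 1 Days 2 to 4, in washout and after Period 2 Day 6 would then belong to no group, although Section 8.3.1 collects them.
- *The whole of each period.* Period 2 runs from Day 1 through follow-up. This is the more natural reading, because every AE then has a group.

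Under both readings Days 1 to 3 and Day 4 onwards share one group. RO7049389 doses before the pitavastatin dose: 3 days x 2 = 6, out of 6 days x 2 = 12.

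**2. Are Days 1 to 3 truly RO7049389 alone?** Washout is at least 7 days from the Period 1 dose (Section 4.1.1), and the mean pitavastatin half-life is about 12 hours (Section 2.2.3). 168 h / 12 h = 14 half-lives, and 2^-14 = 0.006% remains. For practical purposes, yes.

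**3. Direction of the difference.** For a common end point (both to Day 6, or both to Day 34), participants with an AE starting from the Day 4 dose are a subset of those with an AE starting from Day 1. The Period 2 count is therefore at least as large. The two are equal only if everyone with an onset on Days 1 to 3 also has a later one. For example, if 5 of 16 participants had a Period 2 AE, the number with onset after the Day 4 dose could be anything from 0 to 5 (0% to 31%).

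**4. Weight of one participant.** 1/18 = 5.6 percentage points with the 18 planned participants; 1/16 = 6.3 with 16.

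**5. Illustrative range.** The documents give no AE rates, so both cases below are assumptions. Let *a* be the incidence on Days 1 to 3 and *c* the incidence from the Day 4 dose. With independence, Period 2 incidence = 1 - (1 - a)(1 - c).

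| Assumption | c | Period 2 incidence | Excess | Excess x 18 |
|---|---|---|---|---|
| Constant daily rate to Day 34 (3 days before, 30 days after): 1 - (1 - c)^(33/30) | 10% | 10.9% | 0.9 points | 0.2 |
| Same | 20% | 21.8% | 1.8 points | 0.3 |
| AEs only on the 6 dosing days, equal daily rate (a = c): 1 - (1 - c)^2 | 10% | 19% | 9 points | 1.6 |
| Same | 20% | 36% | 16 points | 2.9 |

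If no AE starts on Days 1 to 3, the excess is zero.

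**6. Where should a combination window end?** Period 2 safety laboratory samples after Day -1 fall on Day 4, Day 7 and the follow-up visit (Table 1 of Section 1.3). Section 8.10.2 places assessments on dosing days before dosing unless otherwise noted. If that governs the Day 4 sample, Day 7 is the first scheduled laboratory result after the co-dose, about 12 hours after the last RO7049389 dose (note d). A window closed on Day 6 would miss an abnormality first found there. For the same reason, findings from pre-dose Day 4 assessments belong to RO7049389 alone.

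**The case against.** The strongest reply is that the objective names pitavastatin with multiple doses of RO7049389, and the Days 1 to 3 doses are part of those multiple doses. They bring RO7049389 to steady state before pitavastatin is given (Section 4.2). On that view Period 2 is the combination regimen, Period 1 is pitavastatin alone, and grouping by period gives an incidence for each. This stands. A reader might infer that the plan yields no AE incidence for the combination at all; the documents do not support that, because the regimen figure is there. What is missing is the narrower figure for AEs that start after pitavastatin is added.

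A second reply is that treatment period may have been meant as treatment phase. No section says so. If it was meant, the same edit would make it explicit.

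A third is that causality is judged separately for each drug (Appendix 2, Section 3.2). That is useful, but it is a judgement on each event and not an incidence by exposure, and no planned AE table uses it.

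A fourth is practical. A split on the morning of Day 4 needs onset timing, and the AE text speaks of dates only. This also stands, and the fix has to allow for onsets that cannot be placed.

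**Conclusion.** The point holds in a limited form. The planned AE table describes the Period 2 regimen as a whole but cannot show AEs with onset after the Day 4 co-dose, and its Period 2 count is an upper bound for those. The conclusion rests on the documents' own use of period and treatment period, since Section 9.4.2 gives no definition. The direction is certain for counts to a common end point. The size is unknown and may be small: 5.6 percentage points for each participant whose only Period 2 AE starts on Days 1 to 3, with 18 participants.

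Three further inferences would go too far:
- That the Period 2 figure will be materially inflated. No AE rates are documented, and the assumed cases above run from 0.2 to 2.9 participants of 18.
- That a split would isolate an interaction. The phases follow a fixed order, differ in length and are only described.
- That the trial's main conclusion is at risk. Summaries are descriptive (Section 9), there are no hypotheses (Section 9.1), and the primary pharmacokinetic analysis does not use AE data.

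This is a cheap improvement of low priority.

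**What to change.** In the AE row of Table 6, summarise AEs by treatment at onset:
1. Pitavastatin alone: from the Period 1 dose to before the first RO7049389 dose (about 7 to 21 days).
2. RO7049389 alone: from the first Period 2 dose to before the Day 4 pitavastatin dose (about 3 days).
3. Combination: from the Day 4 pitavastatin dose to the end of AE collection, 28 days after the last dose (about 30 days). Show onsets after Day 7 also as a follow-up subset.

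Use the participants who entered each phase as denominators. The safety population is anyone dosed with either drug, and no per-period denominator is given, so someone who stops on Days 1 to 3 could otherwise be counted without having received both drugs. State the phase lengths, because raw incidences over unequal windows are not directly comparable.

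Place Day 4 onsets by whether they were noted before or after the pitavastatin dose. Findings from pre-dose Day 4 assessments go to RO7049389 alone, and onsets that cannot be placed are flagged in the listing. Also flag AEs that start before the Day 4 dose and persist after it. Keep the by-period table as supplementary.

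Cost: one reworded row, one derived phase variable and the listing flags, with no new visits, samples or procedures. The downsides are small counts per phase, a little more tabulation, and the need to record whether Day 4 onsets came before or after the pitavastatin dose.
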